5.3.4. Supplementary Estimand Analyses

5.3.4.1. Supplementary Analysis 1 (Supplementary Estimand 1, Hypothetical Strategy Estimand)

The primary endpoint will be analyzed using the Hypothetical Estimand for ICES 1-4 (see Section 5.3.2.2.1). Under this estimand, data after an ICE will be set as missing and missing data will be imputed using multiple imputations by fully conditional specification (FCS).

More specifically, the missing GC-free remission response status at Week 28 will be imputed using the FCS logistic regression including intervention group, the baseline disease status (new-onset and relapsing GCA), the baseline GC dose (≤ 30 mg/day or > 30 mg/day), and remission response status as defined in Section 5.5.1.3 starting from Week 4 in the model with seed = 1231 and 500 imputations.

The proportion difference of GC-free remission at Week 28 adjusted for the baseline disease status (new-onset and relapsing GCA), and the baseline GC dose (≤ 30 mg/day or > 30 mg/day) using Mantel-Haenszel weight between the guselkumab group and the placebo group and its 90% CI combining multiple datasets will be provided. Each imputed dataset will be analyzed by CMH test stratified by baseline disease status (new-onset and relapsing GCA), and the baseline GC dose (≤ 30 mg/day or > 30 mg/day).

The values of the general association test statistics from the CMH test for each imputed dataset will be transformed using the Wilson-Hilferty transformation to create a more normal distributed statistic:

$$Z = \frac{(CMH)^{(1/3)} - 7/9}{(2/9)^{(1/2)}}.$$

The resulting transformed values will be combined using SAS PROC MIANALYZE and obtain overall p-value for the CMH test.

5.3.4.2. Supplementary Analysis 2 (Supplementary Estimand 2, Treatment Policy Estimand)

The primary endpoint will be analyzed utilizing the Treatment Policy (de Facto) Estimand. For participants who experience an intercurrent event through Week 28, the analysis will be performed using observed data regardless of intercurrent events. Missing data will not be imputed. The Cochran-Mantel-Haenszel chi-square statistic stratified by baseline disease status (new-onset and relapsing GCA), and the baseline GC dose (≤ 30 mg/day or > 30 mg/day) at a 2-sided significance level of 0.10 will be used. Difference in response rates between the 2 study intervention groups at Week 28 adjusted for baseline disease status (new-onset and relapsing GCA), and the baseline GC dose (≤ 30 mg/day or > 30 mg/day) using Mantel-Haenszel weight and the corresponding 90% CI will be presented.

5.3.4.3. Supplementary Analysis 3 (Supplementary Estimand 2, Treatment Policy Estimand [Sensitivity Analysis])

The primary endpoint will be analyzed utilizing the Treatment Policy Estimand. For participants who experience an intercurrent event through Week 28, the analysis will be performed using observed data regardless of intercurrent events.

The same missing data handling rules and analysis methods specified in Section 5.3.4.1 for Supplementary Analysis 1 (Hypothetical Strategy Estimand) will be applied.

5.3.4.4. Supplementary Analysis 4 (Supplementary Estimand 2, Treatment Policy Estimand)

A generalized linear model with logit link for binary repeated measurement data will be performed on the primary endpoint after applying the Treatment Policy to ICEs. The model will include the intervention group, baseline disease status (new-onset and relapsing GCA), and the baseline GC dose (≤ 30 mg/day or > 30 mg/day), visit, and intervention and visit interaction in the model. The derived odds ratio on GC-free remission at Week 28 and its 2-sided 90% CI will be provided. In addition, the proportion difference of GC-free remission response at Week 28 between the guselkumab and the placebo group and its 2-sided 90% CI will also be provided. Missing data will not be imputed and will be handled by the model under missing at random assumption.

5.3.5. Per Protocol Analysis

The primary analyses for primary endpoint will also be performed on per protocol analysis set (Section 4). The same data handling rules specified in Section 5.3.2 and Section 5.3.3 will be applied.

5.4. Secondary Endpoints Analysis

5.4.1. Secondary Endpoints

Objective: To evaluate the efficacy of guselkumab with a comparison to placebo, in combination with a 26-week GC taper regimen, in adult participants with new-onset or relapsing GCA for the following secondary endpoints:

1. The proportion of participants achieving GC-free remission from Week 28 through Week 52 by visit
2. The proportion of participants achieving GC-free remission and normalization of ESR at Week 28 and from Week 28 through Week 52 by visit
3. The proportion of participants achieving GC-free remission and normalization of CRP at Week 28 and from Week 28 through Week 52 by visit
4. The proportion of participants achieving GC-free remission and normalization of both ESR and CRP at Week 28 and from Week 28 through Week 52 by visit
5. The cumulative GC dose through Week 28 and through Week 52

6. The time to first GCA disease flare or discontinuation of study intervention due to AE of worsening of GCA through Week 28 and through Week 52
7. The number of GCA disease flares or discontinuation of study intervention due to AE of worsening of GCA through Week 28 and through Week 52

5.4.1.1. Definition of Endpoints

5.4.1.1.1. GC-free Remission at Each Timepoint from Week 28 through Week 52

1. No signs or symptoms of active GCA at timepoint Week X
AND
2. Absence of GCA flare from first dose of the study agent through Week X
AND
3. Adherence to the protocol specified 26-week GC taper

5.4.1.1.2. GC-free Remission and Normalization of ESR at Week 28 and from Week 28 through Week 52 by Visit

1. No signs or symptoms of active GCA at timepoint Week X
AND
2. Absence of GCA flare from first dose of the study agent through Week X, inclusive,
AND
3. Adherence to the protocol specified 26-week GC taper
AND
4. Normalization of ESR is defined as ESR <30 mm/hr at Week X.

5.4.1.1.3. GC-free Remission and Normalization of CRP at Week 28 and from Week 28 through Week 52 by Visit

1. No signs or symptoms of active GCA at timepoint Week X
AND
2. Absence of GCA flare from first dose of the study agent through Week X, inclusive,
AND
3. Adherence to the protocol specified 26-week GC taper,
AND
4. Normalization of CRP is defined as CRP <10 mg/L or <1 mg/dL.

5.4.1.1.4. Cumulative GC Dose

The total cumulative GC dose administered will include GCA taper, GC rescue therapy as well as for all other indications (any oral GC) from first dose of the study agent to Week 28 or Week 52.

5.4.1.1.5. Time to First GCA Disease Flare or Discontinuation of Study Intervention due to AE of Worsening of GCA

Time to occurrence of GCA disease flare is defined as the time from first dose of the study agent to the occurrence of the first observation of GCA disease flare or discontinuation due to AE of worsening of GCA.

The definition of GCA disease flare is defined in Section 5.3.1.

5.4.1.1.6. Number of GCA Disease Flares or Discontinuation of Study Intervention due to AE of Worsening of GCA

The number of GCA disease flares or discontinuation of study intervention due to AE of worsening of GCA is the total number of flares or discontinuation of study intervention due to AE of worsening of GCA participants experience from first dose of the study agent through Week 28 or through Week 52.

The definition of GCA disease flare is defined in Section 5.3.1.

5.4.1.2. Estimands

The study intervention and population are the same as the primary estimand. The following table provides the list of variables, summary measure (population-level summary) and intercurrent event for secondary endpoints.

Table 2: List of Secondary Endpoints and Estimands

Estimands	Variable	Summary Measure (Population-level summary)	Intercurrent Events
Sec 1	Binary response variable, where a responder is defined as a participant achieving GC-free remission from Week 28 through Week 52 by visit	Difference in the proportions of achieving GC-free remission between the guselkumab groups and the placebo group	Using the same analysis strategies as the primary estimand.
Sec 2	Binary responder variable, where a responder is defined as a participant achieving GC-free remission and normalization of ESR at Week 28 and from Week 28 through Week 52 by visit	Difference in the proportions of achieving GC-free remission and normalization of ESR between the guselkumab group and the placebo group	
 The analysis strategies for the Week 28 endpoint will be the same as those for the primary estimand. The analysis strategies for summary over time by visit from Week 28 through Week 52 are the same as those in #1 in this table.

Estimands	Variable	Summary Measure (Population-level summary)	Intercurrent Events
Sec 3	Binary response variable, where a responder is defined as a participant achieving GC-free remission and normalization of CRP at Week 28 and from Week 28 through Week 52 by visit	Difference in the proportions of achieving GC-free remission and normalization of CRP between the guselkumab group and the placebo group	
 1. The analysis strategies for the Week 28 endpoint will be the same as those for the primary estimand. 2. The analysis strategies for summary over time are the same as those in #1 in this table.
Sec 4	Binary response variable, where a responder is defined as a participant achieving GC-free remission and normalization of both ESR and CRP at Week 28 and from Week 28 through Week 52 by visit	Difference in the proportion of achieving GC-free remission and normalization of both ESR and CRP between the guselkumab group and the placebo group	
 1. The analysis strategies for the Week 28 endpoint will be the same as those for the primary estimand. 2. The analysis strategies for summary over time by visit from Week 28 through Week 52 are the same as those in #1 in this table.
Sec 5	Cumulative GC dose through Week 28 and through Week 52	Descriptive statistics for the guselkumab group and the placebo group	Treatment Policy strategy will be used regardless of the ICEs.
Sec 6	Time to first GCA disease flare or discontinuation of study intervention due to AE of worsening of GCA through Week 28 and through Week 52	Hazard ratio of the guselkumab group vs. the placebo group	Treatment Policy strategy will be used regardless of the ICEs.
Sec 7	Number of GCA disease flares or discontinuation of study intervention due to AE of worsening of GCA through Week 28 and through Week 52	Descriptive statistics for the guselkumab group and the placebo group	Treatment Policy strategy will be used regardless of the ICEs.

5.4.1.3. Analysis Methods

Unless otherwise specified, the analysis population will be the FAS defined in Section 4. The endpoints will be summarized by intervention group.

Simple descriptive statistics, such as n, mean, SD, median, IQ range, minimum and maximum for continuous variables and counts and percentages for discrete variables will be used to summarize most data, if appropriate.

5.4.1.3.1. Binary Endpoints (Secondary Endpoints 1 - 4)

Analyses for binary secondary endpoints (proportion of responders) at Week 28 will be the same as the primary endpoint.

For secondary binary endpoints at Week 28, Cochran-Mantel-Haenszel chi-square statistic stratified by baseline disease status (new-onset and relapsing GCA), and the baseline GC dose (≤ 30 mg/day or > 30 mg/day) at a 2-sided significance level of 0.10 will be used to compare between the guselkumab and the placebo groups. Difference in response rates between the 2 intervention groups at Week 28 adjusted for baseline disease status (new-onset and relapsing GCA), and the baseline GC dose (≤ 30 mg/day or > 30 mg/day) using Mantel-Haenszel weight and the corresponding 90% CI will be presented.

For the summary over time by visit, after accounting for the ICEs for the primary estimand, any missing data for an endpoint will be imputed as not achieving the associated binary endpoints at Week X.

5.4.1.3.2. Continuous Endpoint (Secondary Endpoints 5, 7)

Analyses for continuous endpoints will be based upon the Treatment Policy estimand. If a participant experiences an intercurrent event, the intercurrent event does not affect the outcome, and the data collected at and after the event will be used for analysis. Missing data will not be imputed.

The total cumulative glucocorticoid dose will be compared between the guselkumab and the placebo groups using van Elteren test stratified by baseline disease status (new-onset and relapsing GCA) and baseline GC dose (≤ 30 mg/day or > 30 mg/day) at Week 28.

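### Secondary endpoint 7 counts flares with no allowance for time at risk and no rule for participants who leave the study early

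*SAP*

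**What the plan says.** SAP 5.4.1 lists secondary endpoint 7 as "The number of GCA disease flares or discontinuation of study intervention due to AE of worsening of GCA through Week 28 and through Week 52". SAP 5.4.1.1.6 derives it as a raw total that runs from the first administration up to Week 28 or Week 52: the endpoint "is the total number of flares or discontinuation of study intervention due to AE of worsening of GCA participants experience from first dose of the" …

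The analysis is set in three places:

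- SAP 5.4.1.3.2 groups the endpoint with cumulative GC dose, under the heading "Continuous Endpoint (Secondary Endpoints 5, 7". The section applies the treatment policy strategy and adds "Missing data will not be imputed". The one test it names, van Elteren, is for cumulative GC dose.
- SAP Table 2 (5.4.1.2) gives the summary measure for endpoint 7 as "Descriptive statistics for the guselkumab group and the placebo group" and, for intercurrent events, "Treatment Policy strategy will be used regardless of the ICEs".
- SAP 5.4.1.3 spells out the descriptive statistics: "Simple descriptive statistics, such as n, mean, SD, median, IQ range, minimum and maximum for continuous variables", with counts and percentages for discrete variables.

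Nowhere does the SAP give endpoint 7 a person-time rate, an offset, a count model or a rule for participants who leave before the end of the window. Protocol 9.4.3 leaves the details of the secondary analyses to the SAP.

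**The concern.** A count of events means little without the time over which the events could occur. The planned window is the same for everyone, but Protocol 7.2 allows exit through withdrawal of consent, loss to follow-up or death, and no assessments are allowed after consent is withdrawn. Protocol 9.2 anticipates some attrition. The treatment policy strategy does not help after study exit, because it can use only data that were collected.

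Flare prevention is part of the secondary efficacy objective, and endpoint 7 is the only secondary endpoint that captures repeat flares. Repeat flares are foreseen: Protocol 4.1 provides for visits at subsequent flares, and Protocol 6.8.3 lets participants stay on blinded study agent after rescue. If the arms lose participants at different rates, a mean count can differ between them for reasons unrelated to flaring.

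**Working it through.** The documents state no flare rate, dropout rate or power for endpoint 7, so there is no plan figure to reproduce. Everything below is illustration under stated assumptions.

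**Inputs.** Window T = 28 or 52 weeks (SAP 5.4.1). Planned arms of 34 and 17 (SAP 3). Assumed: a constant flare rate, a share d of an arm leaving the study, and exit at week w.

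**Step 1: two readings of the SAP.** Under reading A an early leaver enters with the count so far. Under reading B an early leaver has no value and drops out of the summary. The instruction not to impute missing data fits either.

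**Step 2: reading A, one arm.** Observed mean ÷ full-follow-up mean = [(1 − d)T + d·w] ÷ T = 1 − d(1 − w/T). The flare rate and the length of the window cancel.

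| Share leaving (d) | Exit at half the window | Exit at a quarter of the window |
|---|---|---|
| 5% | 0.975 | 0.9625 |
| 10% | 0.950 | 0.925 |
| 20% | 0.900 | 0.850 |
| 30% | 0.850 | 0.775 |

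So 10% to 30% withdrawal lowers the arm's mean by 5% (1 − 0.950) to 22.5% (1 − 0.775).

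**Step 3: reading A, two arms with equal true rates.** Assume 1 flare per 52 weeks in both arms, with 8 of 34 guselkumab and 1 of 17 placebo participants leaving at Week 12.

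- Through Week 52, guselkumab: 26×52 + 8×12 = 1448 weeks; 1448/52/34 = 0.82 flares per participant.
- Through Week 52, placebo: 16×52 + 1×12 = 844 weeks; 844/52/17 = 0.95. Ratio of means 0.86.
- Through Week 28: 26×28 + 8×12 = 824 weeks gives 0.47; 16×28 + 1×12 = 460 weeks gives 0.52. Ratio 0.90.
- Events divided by participant-time: rate ratio 1.00 in both windows. This follows from the constant-rate assumption.

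**Step 4: direction.** Exchange the dropout shares, so that 2 of 34 leave on guselkumab and 4 of 17 on placebo. The Week 52 means become 0.95 and 0.82, and the ratio 1/0.858 = 1.17, now against guselkumab. With equal shares and timing the factor in Step 2 cancels and the ratio is 1.00.

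**Step 5: size against noise.** In the Week 52 example, with Poisson variance, the distortion is 0.955 − 0.819 = 0.136. The standard error of the difference is √(0.819/34 + 0.955/17) = 0.283. The distortion is about 0.5 standard errors.

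**Step 6: reading B.** In the same example the summary rests on 26 and 16 completers. An expected 8×12/52 = 1.8 guselkumab events and 1×12/52 = 0.2 placebo events are discarded. The completers' mean is unbiased only if leaving is unrelated to flaring.

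**The case against.** The case for leaving the plan alone is a fair one.

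- **Follow-up is mostly protected.** Participants who only stop treatment keep attending planned visits (Protocol 1.3 footnote; Protocol 7.1 words this as an option), and their later data count. A treatment stop for worsening GCA is itself an event, so that kind of exit raises the count. This stands: time at risk is cut short only by leaving the study.
- **Flare outcomes are compared elsewhere.** Endpoint 6 covers the same composite with a Cox hazard ratio, log-rank test and Kaplan-Meier curves (SAP 5.4.1.3.3), methods that ordinarily censor early leavers, though the SAP states no censoring rule. Endpoints 1 to 4 require absence of flare and treat missing data as failure (SAP 5.4.1.1 and 5.4.1.3.1). A reader might infer that flare prevention is left without any treatment comparison; these sections show otherwise. None of them, however, summarises repeat flares.
- **Descriptive treatment is reasonable with 51 participants.** The wording of SAP 5.4.1.3 does not rule out tabulating the counts. This stands, but a descriptive summary still needs a defined denominator. SAP 5.7.1 summarises average follow-up only for the safety tables.
- **A rate is not a complete cure.** GC is tapered to zero by Week 26 (Protocol 10.8), and Protocol 2.1.1 describes relapse as common during taper. If the hazard changes over time and early dropout is unequal, a person-time rate is distorted too. This stands, and is why a model should be optional.

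**Conclusion.** The gap is real but small. Endpoint 7 is a count without a time-at-risk denominator and without a rule for early leavers. Under the count-so-far reading, 10% to 30% withdrawal at a quarter to a half of the window lowers an arm's mean by 5% to 22.5%. Under the exclusion reading the summary is completers-only. The percentages rest on an assumed constant flare rate and assumed dropout.

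Two stronger conclusions are tempting and not supported:

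- That the SAP scores someone who leaves flare-free at Week 4 as having zero flares through Week 52. It states no such rule; the defect is the silence.
- That the plan flatters guselkumab by a known amount. The documents give no dropout rates, the direction depends on which arm loses more people, and equal withdrawal has no effect on the ratio.

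No test is named for endpoint 7 and no decision rests on it. What is at stake is a misleading description of repeat flares, not a false p-value. This is a cheap improvement, not a flaw in the trial's main inference.

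**What to change.** In SAP 5.4.1.3.2 and Table 2:

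1. State that every FAS participant contributes events and follow-up time from first dose to study exit or Week 28/Week 52, whichever comes first.
2. Report by arm the total events, participant-years and events per participant-year, with the distribution of 0, 1 and 2 or more events. Show Week 0–28 and Week 0–52 separately, because the hazard may differ during and after the taper.
3. Optionally, as supportive only and if it converges, add a rate ratio with 90% CI from a Poisson model with robust variance or a negative binomial model, with log follow-up as offset and the two stratification factors.

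The cost is a few sentences of SAP text and a few lines of programming, with no new data collection. The downsides are few events, wide intervals, a rate that assumes a roughly constant flare hazard, and no protection against dropout that is itself related to flaring.

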Relapsing GCA: diagnosis of GCA >6 weeks before first study intervention and in the meantime achieved remission (absence of signs and symptoms attributable to GCA and normalization of ESR (<30 mm/hr) and CRP (<10 mg/L or <1 mg/dL) included) including previous treatment with ≥ 40 mg/day prednisolone (or equivalent) for ≥ 2 weeks.

* The 6-week time window must be calculated from the date of suspected GCA diagnosis. Suspected diagnosis is defined as the date when GC therapy was initiated to treat suspected GCA.

6. Criterion modified per Amendment 2

- 6.1. Have active GCA within 6 weeks of first study intervention

Active GCA: presence of signs and symptoms of GCA (Domain I, see Section 10.5) and elevated ESR ≥ 30 mm/hr, or CRP ≥ 10 mg/L (or 1 mg/dL), attributed to active GCA.

ESR ≥ 30 mm/hour or CRP ≥ 10 mg/L (or 1 mg/dL) is not required if active GCA has been confirmed by a positive temporal artery biopsy or ultrasound or other imaging modality (see inclusion criterion 4) within 6 weeks of first study intervention

Concomitant or previous medical therapies received

7. At screening, receiving oral GC treatment with a minimum dose of 20 mg/day and maximum dose of 60 mg/day (prednisone or equivalent) for the treatment of active GCA.
8. Clinically stable GCA disease on a GC dose between 20 and 60 mg/day (prednisone or equivalent) at randomization such that the participant is able to safely participate in the protocol defined prednisone taper regimen, in the opinion of the investigator.

Contraception

9. A woman must be:

Not of childbearing potential

OR

Of childbearing potential and

Practicing a highly effective method of contraception (failure rate of <1% per year when used consistently and correctly) and agrees to remain on a highly effective method while receiving study intervention and until 12 weeks after last dose - the end of relevant systemic exposure.

Definitions of childbearing potential and examples of highly effective methods of contraception are located in Section 10.7.

10. A woman of childbearing potential must have a negative urine pregnancy test at screening and at Week 0 prior to administration of study intervention.
11. A woman must agree not to donate eggs (ova, oocytes) for the purposes of assisted reproduction during the study and for at least 12 weeks after receiving the last administration of study intervention.

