10.8. Appendix 8: Protocol Defined 26-Week Glucocorticoid Taper

Table 3: Protocol Defined 26-Week Glucocorticoid Taper[#]

[figure not shown]
Week	Initial prednisone ⁺ dose at Randomization (*)			
	60-50 mg	49-40 mg	39-30 mg	29-20 mg
	Daily dose (mg/day)	Daily dose (mg/day)	Daily dose (mg/day)	Daily dose (mg/day)
0 ^{**}	60-50	49-40	39-30	29-20
1	50	40	30	20
2	40	35	25	20
3	35	30	20	17.5
4	30	25	20	17.5
5	25	20	17.5	17.5
6	20	17.5	17.5	15
7	17.5	15	15	15
8	15	15	15	15
9	12.5	12.5	12.5	12.5
10	12.5	12.5	12.5	12.5
11	10	10	10	10
12	10	10	10	10
13	9	9	9	9
14	8	8	8	8
15	7	7	7	7
16	6	6	6	6
17	6	6	6	6
18	5	5	5	5
19	5	5	5	5
20	4	4	4	4
21	4	4	4	4
22	3	3	3	3
23	3	3	3	3
24	2	2	2	2
25	1	1	1	1
26	0	0	0	0
27	0	0	0	0
28	Primary Endpoint Assessment Week 28			

- * Individual participants will be receiving different doses of prednisone (or equivalent) at specified time points, depending on their initial GC dose at randomization. Therefore, the tapering schedule indicates the required decrease in prednisone dose on a weekly basis, with the specific week varying by individual participant.

- ** The first week (Week 0) after randomization the participant will take their initial GC dose, and per Week 1 start with their taper in accordance with this table and their initial starting dose.
- + If the participant continues on GC other than prednisone or prednisolone, the Investigator should contact the Sponsor to ensure that the taper is appropriately adjusted for the GC equivalency compared with prednisone, using the Appendix 10 conversion table to convert the Prednisone Taper doses to the equivalent alternate glucocorticoid.
- # In countries where not all required tablet strengths are available to comply with the lower doses of the protocol-defined taper, where authorized (ie, HA and Ethics Committee approval in place), small variations in daily steroid dose of up to 0.5 mg/day are allowed to make the taper feasible. Sites that are impacted by this should reach out to the sponsor clinical team for further guidance before any participants start their taper. If tablets need to be cut in half or in quarters this should preferably be performed by site staff.

[figure not shown]

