3. SAMPLE SIZE DETERMINATION

Approximately 51 participants are planned to be randomized into the study. The assumptions for the sample size and power calculation were based on the data from the Actemra Phase 3 GCA study. In the Actemra Phase 3 study, the proportions of participants in GC-free remission at Week 28 were estimated to be approximately 38% and 74% for placebo (+26-week GC taper) and Actemra qw (+26-week GC-taper), respectively, for a treatment difference of 36%.

Based on the data above, the GC-free remission rates at Week 28 are assumed to be 40% for placebo and 80% for guselkumab treatment arm. Based on these assumptions, 51 participants are planned to be randomized in a 2:1 ratio to either the guselkumab group (N=34) or the placebo

group (N=17). These sample sizes provide the study with 82% power to detect a difference in the primary endpoint between the 2 study intervention groups.

Table 1 shows the power to detect a difference in proportions of participants in GC-free remission between the guselkumab and placebo intervention groups at Week 28 under various assumptions.

Table 1: Power to Detect Difference in Proportions of Participants Achieving Glucocorticoid-free Remission between the Guselkumab and Placebo Intervention Groups at Week 28

Placebo (n = 17)	Guselkumab (n = 34)	Power (%)
35%	70%	68
	75%	81
	80%	90
40%	75%	69
	80%	82
	85%	91

Notes:

- The power calculation is based on two-sample Z test with continuity correction (pooled variance) under the normal distribution approximation.
- Power calculation is based on a 2-sided significance level of 0.10.
- Total sample size is 60.

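### The van Elteren test of cumulative GC dose ranks prescribed taper differences of up to 710.5 mg within a stratum as outcome; it stays valid but gives up some efficiency, and adjusting for planned dose would recover it

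*SAP*

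**What the plan says.** SAP 5.4.1.1.4 defines the outcome: "The total cumulative GC dose administered will include GCA taper, GC rescue therapy as well as for all other indications", counting any oral GC from first study dose to Week 28 or Week 52.

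SAP 5.4.1.3.2 names one test for it: "The total cumulative glucocorticoid dose will be compared between the guselkumab and the placebo groups using van Elteren test stratified by baseline disease status". The second stratification factor is baseline GC dose, at or below versus above 30 mg/day, and the test is named for Week 28. No covariate is given. SAP Table 2 otherwise lists only descriptive statistics for this endpoint.

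The taper is in Protocol 10.8, Table 3. It has four columns by starting dose (60-50, 49-40, 39-30 and 29-20 mg), so participants take different doses "at specified time points, depending on their initial GC dose at randomization". The starting dose itself also counts: "The first week (Week 0) after randomization the participant will take their initial GC dose, and per Week 1 start with their taper". Protocol 5.1 sets the entry range: "At screening, receiving oral GC treatment with a minimum dose of 20 mg/day and maximum dose of 60 mg/day".

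**The concern.** Only dose above or below plan can reflect treatment. The planned part is known at randomization, and the 30 mg/day cut does not remove it. The upper stratum contains three taper columns (31-39, 40-49 and 50-60 mg), and the 39-30 column falls in both strata because a start of exactly 30 mg belongs to the lower one.

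A GC-sparing effect is a named secondary objective, and cumulative dose measures it most directly. With 34 and 17 participants, removable noise in the ranks makes a real effect harder to see.

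**Working it through.** **1. Planned totals.** Planned total (mg) = 7 × (starting daily dose for Week 0 + sum of daily doses for Weeks 1 to 27). Weeks 26 and 27 are zero, and all columns are identical from Week 8.

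| Taper column | Daily doses, Weeks 1-8 | Weeks 9-27 | Sum | × 7 |
|---|---|---|---|---|
| 60-50 mg | 232.5 | 108 | 340.5 | 2,383.5 |
| 49-40 mg | 197.5 | 108 | 305.5 | 2,138.5 |
| 39-30 mg | 160 | 108 | 268 | 1,876.0 |
| 29-20 mg | 137.5 | 108 | 245.5 | 1,718.5 |

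Adding 7 × starting dose:

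| Start (mg/day) | Planned total (mg) | Stratum |
|---|---|---|
| 20 | 140 + 1,718.5 = 1,858.5 | ≤30 |
| 30 | 210 + 1,876.0 = 2,086.0 | ≤30 |
| 31 | 217 + 1,876.0 = 2,093.0 | >30 |
| 35 | 245 + 1,876.0 = 2,121.0 | >30 |
| 40 | 280 + 2,138.5 = 2,418.5 | >30 |
| 50 | 350 + 2,383.5 = 2,733.5 | >30 |
| 60 | 420 + 2,383.5 = 2,803.5 | >30 |

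**2. Spread left inside a stratum.**
- Above 30 mg/day: 2,803.5 − 2,093.0 = 710.5 mg. Of this, 7 × (60 − 31) = 203 mg is the held Week 0 dose and 2,383.5 − 1,876.0 = 507.5 mg is the difference between columns.
- At or below 30 mg/day: 2,086.0 − 1,858.5 = 227.5 mg.

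**3. Effect on ranks.** Take two participants with the same disease status in the upper stratum. One starts at 60 mg and follows the taper exactly. The other starts at 35 mg and is rescued. The first still ranks worse whenever the rescue adds less than 2,803.5 − 2,121.0 = 682.5 mg.

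**4. Power.** The plan states no power for this endpoint. Its 82% for the primary endpoint does reproduce. The pooled proportion is (17 × 0.40 + 34 × 0.80)/51 = 0.667, the null SE 0.1400, the alternative SE 0.1372 and the continuity correction 0.5 × (1/17 + 1/34) = 0.0441. Power is Φ[(0.40 − 0.0441 − 1.645 × 0.1400)/0.1372] = Φ(0.915) = 82.0%.

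For cumulative dose, simulation is needed. Taken from the plan: 34 vs 17, four strata, and two-sided 0.10 ("Power calculation is based on a 2-sided significance level of 0.10"). Assumed: rescue in 60% vs 20%, the complements of the planning rates ("the GC-free remission rates at Week 28 are assumed to be 40% for placebo and 80% for guselkumab treatment arm"). The starting-dose mix, flare timing, rescue course and random variation in dose taken are also assumptions. Rescue is at the investigator's discretion (Protocol 6.8.3).

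Gain of stratified rank ANCOVA on planned dose over the SAP test, in points of power:

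| Assumed rescue | Starting doses | SD of dose taken | Gain |
|---|---|---|---|
| 15-40 mg/day, falling 2.5 mg/week | four mixes | 0% | +7 to +13 |
| same | four mixes | 2% | +4 to +10 |
| same | four mixes | 5% | +4 to +7 |
| same | four mixes | 10% | 0 to +2 |
| 15-40 mg/day | even over 20-60 | 5% or 10% | +5 to +7 |
| 15-40 mg/day | mostly 20-30 | 5% or 10% | +1 to +4 |
| 40-60 mg/day | three mixes | 5% or 10% | 0 to +4 |
| small and late | even over 20-60 | 5% or 10% | +6 to +14 |
| small and late | mostly 20-30 | 5% or 10% | 0 to +3 |

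The upper rows (1,500 trials per scenario) and the lower rows (1,200) are separate sets of runs. The Monte Carlo standard error of each power estimate is about 1.2 to 1.3 points, so rows should not be compared finely. No run showed a loss beyond simulation error.

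In a further set with flares in Weeks 4-26, the SAP test itself had about 58% to 79% power. Its rejection rate under the null was 9.4% in 2,000 trials, against a nominal 10%.

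**5. Two other remedies.**
- Ranking actual minus planned dose gained about +10 to +25 points with exact adherence and about 0 to +10 with 5% variation. In another set it ranged from −1 to +17, and was about zero when rescue doses were larger.
- Stratifying by disease status × four taper columns ranged from −6 to +12. It makes eight strata, 51/8 ≈ 6 participants each.

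**The case against.** A van Elteren test stratified by the randomization factors is a conventional choice, and it is valid here. Baseline GC dose is already a stratum, and SAP 5.5 also summarizes cumulative dose by baseline GC dose and by disease status. The endpoint is secondary, with nominal p-values, no multiplicity control and no power target. Protocol 9.4.1 names ANCOVA for continuous endpoints in general, and 9.4.3 leaves the details to the SAP.

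Most of this stands, and it limits the point to efficiency. It does not remove it. A two-level stratum does not absorb a four-column taper, the extra summaries are not tests, and the SAP's specific test takes up no covariate.

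Three stronger readings are tempting, and the documents support none of them:
- **A definite power loss, say 5 to 9 points.** Such values are mid-range results under particular assumptions. The documents give no starting-dose distribution, rescue regimen or adherence figure.
- **The prescribed spread is as large as a typical rescue course.** That sets an extreme range (start 60 vs 31) against a mean. In one simulated setting the planned-dose SD within strata was 107 mg (≤30) and 226 mg (>30), against a mean rescue excess of 789 mg: 107/789 ≈ 14% and 226/789 ≈ 29%. The 682.5 mg in the 60-versus-35 example is also below that mean.
- **The comparison is biased or its type I error is inflated.** Randomization is stratified at the same cut, and null rejection stays near 10%.

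**Conclusion.** The point holds as an efficiency loss on a secondary endpoint. The document-based part is exact: up to 710.5 mg (above 30 mg/day) and 227.5 mg (at or below) of planned dose is ranked as outcome within a stratum.

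The power cost against rank ANCOVA on planned dose is about 0 to 14 points, conditional on 60% vs 20% rescue and on the assumed starting doses, rescue course and adherence. It is largest when rescue is small and starting doses are widely spread. It is near zero when rescue doses are large, starts cluster at 20-30 mg, or dose taken varies by about 10%. Confidence is high in the mechanism and moderate in the size.

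**What to change.** In SAP 5.4.1.3.2, keep the endpoint, the two stratification factors and the descriptive totals. Replace the unadjusted van Elteren test with a stratified rank ANCOVA (extended van Elteren): rank total dose and planned dose within strata, regress the first on the second, and apply the stratified mean-score test to the residuals. The covariate is planned cumulative GC dose, derived from starting dose and taper column at randomization. State in advance whether the slope is fitted per stratum or pooled, since 51/4 leaves about 13 participants per stratum.

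Actual minus planned dose may be shown as a supportive analysis only, because it changes the variable being ranked and its gain disappears with larger rescue doses. Splitting the strata by taper column is not advised, as it can lose power.

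The cost is SAP wording. The planned dose is already needed as the denominator of the compliance formula in SAP 5.3.1, and no new data are collected. The change should be made before the Week 28 database lock, by which Protocol 9.4 requires the SAP to be final.
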